#### **6.4 Off study assessment four weeks and 6 months after last dose of study drug.**

Subjects who go off study drug due for any reason listed in section 8.6 will be monitored according to the following schedule. At a minimum, subjects must be evaluated at the NIH Clinical Center at 1 month (+/- 1 week) and 6 months (+/- 2 weeks) after the last dose of study medication. The following studies will be performed:

- Clinical Assessment (1 and 6 months)
- CBC with differential (1 and 6 months at NIH and weeks 1, 2 and 3 at home doctor or NIH)
- Acute care, mineral and hepatic panels, CK, LDH, total protein and uric acid (1 and 6 months at NIH and weeks 1, 2 and 3 at home doctor or NIH)
- Reticulocyte count (1 and 6 months at NIH and weeks 1, 2 and 3 at home doctor or NIH)
- Peripheral blood smear (1 and 6 months at NIH and monthly at home doctor if available till seen at NIH)
- Coagulation and thrombosis screens (PT, PTT) (1 month)
- Bone marrow biopsy with reticulin and collagen staining and aspiration with cytogenetics and flow cytometry (flow cytometry at clinician discretion) (6 months)
- Flow cytometry of peripheral blood for GPI (6 months)
- Lymphocyte phenotyping (TBNK flow cytometry, six months +/- 1 week)
- DAT (direct antiglobulin test) at NIH (1 and 6 months, as clinically indicated)
- Type and screen at NIH (1 and 6 months, as clinically indicated)

## **7. ANCILLARY LABORATORY RESEARCH STUDIES**

### **7.1 Collection of samples**

During the course of participating on this study, an additional 10 cc of blood (NIH visits only) and 5 cc of bone marrow aspirate each time a subject has a bone marrow examination may be

requested.

## 7.2 Intended use

These specimens will not be read by a pathologist nor be used for diagnostic purposes. Studies will not be used in assessing the primary endpoint but will be undertaken for descriptive or exploratory ancillary research. The following laboratory research studies may be done and if done, may be correlated with the presence or absence of response:

- Hematopoietic progenitor colony formation and long term-culture-initiating cell assays
- Assay for cytokines/chemokines and their receptors
- Flow cytometry for hematopoietic progenitor cell phenotyping
- Serum (or plasma) and cells for DNA/RNA extraction, protein analysis, apoptosis assessment
- Additional studies which are approved by the NIH IRB and listed in Appendix D of the protocol may be done on stored samples.
- Thrombopoietin (TPO) level

## 7.3 Tracking

Samples will be ordered and tracked through the CRIS Research Screens. Should a CRIS screen not be available, the NIH form 2803-1 will be completed and will accompany the specimen and be filed in the medical record. Coded biospecimens (NHLBI investigators hold the key that identifies research subjects) to be shared outside of NIH for future research use requires an executed Material Transfer Agreement (MTA) and may require IRB approval if results will be returned and re-identified.

## 7.4 Storage

Research samples will be stored with patient identifiers in the secure laboratory of the principal investigator. Research samples will be stored and tracked in accordance with the NHLBI DIR BSI Policy.

## 7.5 End of study procedures

Samples from consenting subjects will be stored until they are no longer of scientific value or if a subject withdraws consent for their continued use, at which time they will be destroyed.

## 7.6 Loss or destruction of samples

Should we become aware that a major breach in our plan for tracking and storage of samples has occurred, the IRB will be notified.

# 8. BIOSTATISTICAL CONSIDERATIONS

## 8.1 Objectives

**Primary objective** is to assess the efficacy of eltrombopag in low to Int-2 risk MDS subjects with cytopenias. Safety of eltrombopag in this subject population will be assessed concurrently.

**Secondary objectives** include the toxicity profile of extended treatment with eltrombopag (treatment longer than 4 months), reduction in incidence and severity of bleeding episodes, erythroid and neutrophil response, and response following extended access to study drug (treatment longer than 4 months).

Criteria for response to the primary endpoint: A treatment response will be any increase in a cytopenia in the lineage that fulfilled eligibility criteria for enrollment, which is defined as follows. Platelet response is defined as platelet count increases to 20,000/ $\mu$ L above baseline at 16 or 20 weeks, or stable platelet counts with transfusion independence for a minimum of 8 weeks in subjects who were previously transfusion dependent. In the event that a subject is transfused platelets for a count >10,000/ $\mu$ L without a medical indication during the study period, the subject may continue on study drug and the response assessment may be extended for an additional 4 weeks, to week 20, at the discretion of the principal investigator. Subject being evaluated for platelet, erythroid, or neutrophil responses, may have the response assessment extended an additional 4 weeks, to week 20, at the discretion of the principal investigator. Erythroid response for subjects with a pretreatment hemoglobin of less than 9 g/dL will be defined as an increase in hemoglobin by  $\geq 1.5$ g/dL without packed red blood cell (PRBC) transfusion support, or a reduction in the units of PRBC transfusions by at least 50% during the eight consecutive weeks prior to response assessment -compared with the pretreatment transfusion number in the previous 8 weeks. Neutrophil response will be defined in those with a pretreatment absolute neutrophil count (ANC) of  $<0.5 \times 10^9/L$  as at least a 100% increase or an absolute increase  $> 0.5 \times 10^9/L$ . Subjects with a platelet, erythroid, and/or neutrophil response at 16 to 20 weeks may continue study medication (extended access) until they meet an off study criteria. Subjects with erythroid, or neutrophil response at 16 weeks may continue study medication for an additional 4 weeks (to ensure eligibility) prior to being consented for entry into the extended access part of the trial. Patients may remain on the extended access until they meet an off study criteria.

*Transfusion Units:* Single donor apheresis platelets have become the primary source of platelets in the US. Therefore, one transfused, single donor platelet apheresis product is considered 1 unit for protocol purposes. In the rare case that a patient received pooled platelet products, each completed platelet transfusion (1 bag) independent of donor units pooled, will be counted as 1 unit transfused.

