### 3. STUDY DESIGN

The study is designed as a non-randomized, Phase II, dose modification study of the oral TPO-R agonist eltrombopag in subjects with MDS with any cytopenia. The primary endpoint is measured at 16 or 20 weeks. Subjects who cannot tolerate the medication or fail to respond will go off study medication. In the event that a subject is transfused platelets for a count  $>10,000/\mu\text{L}$  without a medical indication during the study period, the subject may continue on study drug and the response assessment may be extended for an additional 4 weeks at the discretion of the principal investigator to ensure eligibility to enter the extended access portion of the trial. Subjects with evidence for a clinical response in any lineage at 16 weeks but not yet meeting full primary endpoint response criteria, and who are tolerating investigational treatment, may receive an additional 4 weeks of eltrombopag and be reassessed after 20 weeks. At that time, if they meet primary endpoint response criteria, they will be eligible to enter the extended access part of the study. If they do not meet primary endpoint response criteria, eltrombopag will be discontinued.

Subjects with response may continue study medication (extended access) at the lowest dosage that maintains stable counts or taken off drug for robust response until they meet off study criteria. If subjects are taken off drug for robust response and maintain response, they will be taken off study after 2 years.

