### 8.3 Sample Size

Because the efficacy of eltrombopag in this subject population is unknown, we would like to reject the treatment as quickly as possible with a small number of subjects if the treatment is not effective. In our past experience with this patient population, a novel treatment with a response rate 30% or more would generally warrant further investigation, while the treatment would be rendered non-effective if it has a response rate of 10% or less. We will use Simon's Two-Stage Minimax Design with a response probability of 10% or less to terminate the treatment and the hypothesized actual response probability of 30% or more. The sample size is determined by testing the null hypothesis  $H_0: p \leq 10\%$  versus the alternative  $H_1: p \geq 30\%$  at a significance level of 0.05 and a power of 0.8. At the first stage, 15 subjects will be accrued. Further accrual will be halted until the all 15 subject reach the 16 to 20 weeks response time point. The null hypothesis will not be rejected if no more than 1 subject responds to the treatment within 16 to 20 weeks. If 2 or more subjects respond to the treatment within 16 to 20 weeks at the first stage, then an additional 10 subjects will be accrued, bringing the total number of subjects to  $n = 25$ . The null hypothesis of  $p \leq 10\%$  will be accepted if the total number of responders within 4 months is 5 or less.

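### Week-20 reassessment for the primary response rests largely on investigator discretion, so the Simon count depends on how often extensions are granted

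*Combined protocol and SAP*

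**What the plan says.** **Endpoint.** Sections 8.1 and 8.2 allow response to be reached at week 16 or by week 20.

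**Who is reassessed at week 20.** The text differs by place:
- Section 8.1 (Objectives): a subject being evaluated for a platelet, erythroid or neutrophil response "may have the response assessment extended an additional 4 weeks, to week 20, at the discretion of the principal investigator". This sentence gives no trigger.
- Section 8.6.2: lack of response takes a subject off study at week 16, or at week 20 if the investigator so decides.
- Precis and Section 3: two narrower routes. One is a platelet transfusion above 10,000/µL without a medical indication, where Section 3 allows the extension "at the discretion of the principal investigator to ensure eligibility to enter the extended access portion of the trial". The other is some evidence of response at week 16, short of the full criteria, in a subject tolerating the drug.
- Sections 8.1 and 8.2: week-16 erythroid or neutrophil responders may also continue for 4 weeks before entering extended access.

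**Visits.** Section 6.2 requires a week-16 (+/- 4 days) evaluation at the clinical center. Week-20 evaluations are needed only for subjects kept on drug to assess response.

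**Decision rule.** Section 8.3 uses a Simon minimax design. A treatment is "rendered non-effective if it has a response rate of 10% or less", while "a novel treatment with a response rate 30% or more would generally warrant further investigation". Stage 1 fails if "no more than 1 subject responds to the treatment within 16 to 20 weeks". The final rule needs 6 or more of 25, but counts responders within four months.

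**Oversight.** Section 3 describes a non-randomized study. Section 9.1 has the principal investigator monitor efficacy data.

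**The concern.** The person who may grant the second look sees the blood counts, and under Sections 8.1 and 8.6.2 no objective condition decides who gets it. The definition is met at either time, and no text cancels a week-16 response that is lost by week 20. Measured against week 16, the extra look therefore works in one direction.

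The go/no-go decision turns on very few subjects. One late responder moves stage 1 from 1/15 (stop) to 2/15 (continue), or the final count from 5/25 (20%) to 6/25 (24%). If extension practice decides that subject, the result partly reflects how extensions were granted. No analysis at a fixed week is planned that would show this.

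**Working it through.** **Inputs from Section 8.3:** null rate 10%, alternative 30%, tested "at a significance level of 0.05 and a power of 0.8"; n1 = 15, continue with 2 or more; n = 25, reject the null with 6 or more.

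**Inputs not in the documents:** f, the share of week-16 non-responders who are extended, and c, the chance that an extended subject then qualifies without a drug effect. Both are assumed below.

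**Step 1. Reproduce the plan's design.**

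P(reject | p) = Σ over x = 2 to 15 of Bin(x; 15, p) × P(Bin(10, p) ≥ 6 − x)

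- p = 0.10: 0.0328
- p = 0.30: 0.8017

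A search over two-stage designs returns the same minimax design (1/15, 5/25). The plan's figures are correct.

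**Step 2. Add a selective second look, taking 10% as the week-16 no-effect rate.**

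Effective rate = 0.10 + 0.90 × f × c

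| f | c | Effective rate | P(reject) |
|---|---|---|---|
| none | – | 10.0% | 0.0328 |
| 10% | 5% | 10.45% | 0.0396 |
| 25% | 5% | 11.125% | 0.0514 |
| 20% | 10% | 11.8% | 0.0652 |
| 50% | 5% | 12.25% | 0.0756 |
| 50% | 10% | 14.5% | 0.1415 |
| 30% | 20% | 15.4% | 0.1740 |
| 50% | 30% | 23.5% | 0.5481 |

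The last two rows are extreme for chance conversion and show only how steep the curve is.

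**Step 3. Find the tolerance.** P(reject) reaches 0.05 at a rate of about 11.05%. Then f × c = (0.1105 − 0.10) / 0.90 ≈ 0.012, so about 1.2% of week-16 non-responders need to convert. With 25 × 0.90 = 22.5 expected non-responders, that is 22.5 × 0.012 ≈ 0.27 conversions per trial on average.

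**Step 4. Price the alternative of counting week 16 only.** Suppose the true rate by week 20 is 30% and some of it arrives after week 16 (assumed):
- 2 points late: week-16 rate 28%, power 0.736
- 5 points late: week-16 rate 25%, power 0.616

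**Step 5. Compare the two windows in Section 8.3.** Stage 1 continues if 2 or more "respond to the treatment within 16 to 20 weeks". The final rule says four months, which is about 17 weeks. Read literally, a week-20 responder counts at stage 1 and may not count at the end.

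**The case against.** The strongest reply is that the 16-to-20-week window is prespecified and built into the stage 1 rule, and that the 10% null is tied to no week. If 10% is the no-effect rate for response anywhere in that window, under the extension practice actually used, type I error is 3.3% and nothing is inflated. If the target were response by week 20 with everyone followed, selective extension would undercount. This stands: the inflation in Step 2 applies only when 10% is read as a week-16 rate. Under either reading the observed rate still depends on who is extended.

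A reader might infer that only week-16 failures hand-picked by the investigator go on to week 20, and that the primary rate is therefore biased upward. The documents do not support that much. Week-16 erythroid and neutrophil responders may also continue, and the Precis and Section 3 name a partial-response route to which no discretion is attached. What remains is a conflict between those passages and the open wording in Sections 8.1 and 8.6.2.

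A reader might also infer from Section 3 that week 20 serves only extended-access eligibility and has no place in the efficacy count. The eligibility phrase belongs to the transfusion route. For partial responders, the same section applies the primary response criteria at week 20.

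Chance conversion may also be uncommon. Section 2.9 sees little sign of unaided recovery in refractory cytopenias, and the transfusion criteria use 8-week windows, which dampen brief fluctuation. Neither point covers the count-based criteria in full, and the margin in Step 3 is small.

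**Conclusion.** The point holds in a limited form. Relative to week 16, a discretionary second look can only add responders, so the reported rate and the false-positive rate depend on how often extensions are granted. With 10% as a week-16 rate, type I error starts at 3.3% and passes 5% at an effective rate of about 11.05%. For extension shares of 25% to 50% and conversion of 5% to 10%, it runs from 5.1% to 14.2%. Those shares are assumptions, so the range is illustrative and not an estimate of bias in this trial.

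Two problems need no assumption: the extension wording conflicts between sections, and Section 8.3 uses different response windows for its two decisions.

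It does not follow that week 16 must become the only primary time point. Dose steps every 2 weeks (Section 5.2) make late response plausible, and Step 4 shows a real power cost if late responders are dropped. This should be corrected in the plan; it does not undermine the design or the sample size.

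**What to change.** 1. Keep the 16-or-20-week endpoint if it is wanted, but state the same response window for the stage 1 rule and the final rule in Section 8.3.
2. Reconcile the extension wording in the Precis and Sections 3, 8.1 and 8.6.2, so that one objective, prespecified rule decides who is reassessed for the primary count. Which clinical condition that should be is for the investigators to settle.
3. Prespecify the week-16 (+/- 4 days) response count for all subjects, compare it with the same 2/15 and 6/25 limits, and report it beside the primary count. If the two counts lead to the same decision, extensions did not drive it; if they differ, the reader can see that they did.

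**Cost:** changes of wording and one more reported analysis, which may look less favourable than the primary count. Section 6.2 already requires the week-16 visit, so visits, sample size and care do not change.

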Subjects will initiate study medication at an oral dose of 50 mg/day (25 mg/day for East Asians), which will be adjusted as clinically indicated to the lowest dose that maintains a stable platelet count  $\geq 20,000/\mu\text{L}$  above baseline while maximizing tolerability. Treatment response will be any increase in a cytopenia, in the lineage that fulfilled eligibility criteria for enrollment and will be defined as: **(a)** platelet count increases to  $20,000/\mu\text{L}$  above baseline at 16 or 20 weeks, or stable platelet counts with transfusion independence for a minimum of 8 weeks in subjects who were previously transfusion dependent; **(b)** erythroid response for subjects with a pretreatment hemoglobin of less than 9 g/dL will be defined as an increase in hemoglobin by  $\geq 1.5\text{g/dL}$  without packed red blood cell (PRBC) transfusion support, or a reduction in the units of PRBC transfusions by at least 50% during the eight consecutive weeks prior to response assessment compared with the pretreatment transfusion number in the previous 8 weeks; **(c)** neutrophil response will be defined in those with a pretreatment absolute neutrophil count (ANC) of  $<0.5 \times 10^9/\text{L}$  as at least a 100% increase or an absolute increase  $> 0.5 \times 10^9/\text{L}$ . Subjects meeting a response may remain on the extended access until they meet an off study criteria or the study is closed.

Subjects with response at 16 or 20 weeks may be consented for entry into the extended access part of the trial. In the event that a subject is transfused platelets for a count  $>10,000/\mu\text{L}$  without a medical indication during the study period, the subject may continue on study drug and the response assessment may be extended for an additional 4 weeks, to week 20, at the discretion of the principal investigator. Subjects with evidence for a clinical response in any lineage at 16 weeks but not yet meeting full primary endpoint response criteria, and who are tolerating investigational treatment, may receive an additional 4 weeks of eltrombopag and be reassessed after 20 weeks. At that time, if they meet primary endpoint response criteria, they will be eligible to enter the extended access part of the study. If they do not meet primary endpoint response criteria, eltrombopag will be discontinued.

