### 4. ELIGIBILITY ASSESSMENT

#### 4.1 Inclusion criteria

- 4.1.1 Diagnosis of MDS, with WHO classification of refractory anemia, refractory cytopenia with unilineage dysplasia (RCUD), RARS, RCMD-RS, or RCMD
- 4.1.2 IPSS risk scores of low, intermediate-1, or intermediate-2.
- 4.1.3 Platelet count  $\leq 30,000/\mu\text{L}$  or platelet-transfusion-dependence (requiring at least 4 platelet transfusions in the 8 weeks prior to study entry); OR hemoglobin less than 9.0 gr/dL or red cell

- transfusion-dependence (requiring at least 4 units of PRBCs in the eight weeks prior to study entry) OR ANC $\leq$ 500
- 4.1.4 Age  $\geq$  18 years old
  - 4.1.5 Treatment naïve or off all other treatments for MDS (except stable dosing of filgrastim (G-CSF), erythropoietin, and transfusion support) for at least four weeks. G-CSF can be used before, during and after the protocol treatment for subjects with documented neutropenia (<500/UL) as long as they meet the criteria for other cytopenias as stated above. G-CSF must be held for 3 weeks prior to enrollment bone marrow biopsy and prior to each study assessment bone marrow biopsy, unless clinically indicated to avoid infections per PI discretion.
  - 4.1.6 Adequate liver function, as evidenced by total serum bilirubin  $\leq$  1.5 times the upper limit of normal (patients with Gilbert's disease are eligible, provided intermittent indirect hyperbilirubinemia, AST or ALT  $\leq$  5 times the upper limit of normal).
  - 4.1.7 A serum creatinine concentration  $\leq$  2 x ULN

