**Dose Adjustments for Patients Entering with Anemia (Hb < 9.0gr/dL or transfusion-dependence)**

Depending on response and/or tolerability, the daily dose may be increased or decreased according to the following rules.

Hemoglobin < 9.0 gr/dL or transfusion dependent at baseline	Dose Adjustment or Response
hemoglobin rise of < 1.5 g/dL.	Increase daily dose by 25 mg (25 mg for East Asians) every 2 weeks to maximum 150mg/day for non- East Asians (75mg/day for East Asians).
$\geq$ 1.5g/dL above baseline but $\leq$ 13g/dL following at least 2 weeks of-eltrombopag	Keep at current dosage.
>13g/dL (untransfused) at any time on study	Decrease dosage by 50% to lowest dosage that maintains Hb $\geq$ 1.5g/dL above baseline.
>15g/uL (untransfused) at any time on study	Discontinue eltrombopag for one week, if Hb<13g/dL restart at 50% of current dose. Phlebotomy may be performed if clinically indicated as determined by the investigator.

If after dose escalation to 150 mg (or a maximum tolerated dose below 150 mg) there is no response within the study period, treatment will be discontinued and subjects will go off study per section 8.6. In the event that a subject is transfused platelets for a count >10,000/ $\mu$ L without a medical indication during the study period, the subject may continue on study drug and the response assessment may be extended for an additional 4 weeks at the discretion of the principal investigator.

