## 8.2 Endpoints

The **primary endpoint** will be the portion of drug responders as defined by changes in the platelet count and/or platelet transfusion requirements or the proportion of subjects who meet erythroid response or neutrophil response criteria Platelet response is defined as platelet count increases to 20,000/ $\mu$ L above baseline at 16 to 20 weeks, or stable platelet counts with transfusion independence for a minimum of 8 weeks. Erythroid response for subjects with a pretreatment hemoglobin of less than 9 g/dL will be defined as an increase in hemoglobin by  $\geq 1.5$ g/dL without packed red blood cell (PRBC) transfusion support, or a reduction in the units of PRBC transfusions by at least 50% during the eight consecutive weeks prior to response assessment - compared with the pretreatment transfusion number in the previous 8 weeks. Neutrophil response will be defined in those with a pretreatment absolute neutrophil count (ANC) of  $<0.5 \times 10^9/L$  as at least a 100% increase or an absolute increase  $> 0.5 \times 10^9/L$ . Subjects with a platelet, erythroid, and/or neutrophil response at 16 to 20 weeks may continue study medication (extended access) until they meet an off study criteria. Subjects with erythroid, or neutrophil response at 16 weeks may continue study medication for an additional 4 weeks (to ensure eligibility) prior to being consented for entry into the extended access part of the trial. Patients may remain on the extended access until they meet an off study criteria.

The toxicity profile will be measured using the CTCAE Version 4.0 criteria.

**Secondary endpoints** will include incidence of grade 2 or higher bleeding events as measured by

CTCAE v. 4.0; changes in serum thrombopoietin level, measured at 16 to 20 weeks; progression to higher risk MDS as measured by IWG criteria; and discontinuation of drug in robust responders enrolled in extended access.

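### As written, a subject who enters only through red-cell transfusion dependence, with pretreatment hemoglobin of 9 g/dL or more, counts in the denominator but cannot be a responder

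*Combined protocol and SAP*

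**What the plan says.** **Entry.** Section 4.1.3 admits a subject on the red-cell lineage in either of two ways: hemoglobin below 9.0 g/dL, or transfusion dependence, described as "requiring at least 4 units of PRBCs in the eight weeks prior to study entry". The second route has no hemoglobin ceiling.

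**Dosing.** The table in 5.2 uses the same either/or population: "Dose Adjustments for Patients Entering with Anemia (Hb < 9.0gr/dL or transfusion-dependence".

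**Erythroid response.** Section 8.1 begins "Erythroid response for subjects with a pretreatment hemoglobin of less than 9 g/dL will be defined as an increase in hemoglobin by" at least 1.5 g/dL without transfusion. The same sentence then offers the alternative limb, "a reduction in the units of PRBC transfusions by at least 50% during the eight consecutive weeks prior to response assessment". The two Precis paragraphs and 8.2 repeat this construction, including the hemoglobin opening.

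**Lineage rule.** The Precis states: "Treatment response will be any increase in a cytopenia, in the lineage that fulfilled eligibility criteria for enrollment". Section 8.1 likewise limits response to an increase "in the lineage that fulfilled eligibility criteria for enrollment". The Precis endpoint paragraph and 8.2 do not repeat the rule.

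**Platelet response, for contrast.** Section 8.1 provides for transfused subjects by name: "with transfusion independence for a minimum of 8 weeks in subjects who were previously transfusion dependent". Section 8.2 is shorter: "stable platelet counts with transfusion independence for a minimum of 8 weeks. Erythroid response for subjects with a pretreatment hemoglobin".

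**Denominator.** Section 8.3 treats subjects as evaluable unless they withdraw for reasons other than lack of efficacy or toxicity. The test is Simon's minimax design: stop after 15 subjects if at most 1 responds; otherwise go to 25 and reject the 10% null with 6 or more responders.

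**The concern.** Take a subject with four or more red-cell units in the past eight weeks, a recent transfusion, a recorded hemoglobin of 9 or above, and no qualifying platelet or neutrophil count. This subject is eligible and is dosed under the anemia table. The erythroid sentence does not cover the subject, and the lineage rule closes the other two lineages. A fall from eight units to none would still be scored as a failure.

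The primary result is a count of responders in 25 with a cut at 6, so one or two fixed failures can change the decision. Transfusion raises hemoglobin, so such a subject is plausible. The plan also does not say which blood count supplies the pretreatment value. Under 6.1, eligibility rests on screening data and may be determined up to 4 weeks before consent, while the blood count is repeated within 72 hours of the first dose. In a transfused subject the two values can lie on either side of 9. Unless this is settled in advance, someone will have to decide how to classify the subject after seeing the outcome.

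**Working it through.** **Step 1. Passages side by side.**

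| Place | Red-cell population |
|---|---|
| 4.1.3 entry | Hb < 9, or at least 4 units in 8 weeks |
| 5.2 anemia dosing | Hb < 9, or transfusion dependence |
| Precis (twice), 8.1, 8.2 erythroid response | pretreatment Hb < 9 only |

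The gap is the subject with transfusion dependence, Hb of 9 or more, and no other qualifying lineage.

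**Step 2. Reproduce the design.** Inputs from 8.3: null 0.10, alternative 0.30, first stage 15 (continue with 2 or more), total 25 (reject with 6 or more). With X1 ~ Bin(15, p) and X2 ~ Bin(10, p),

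R(p) = Σ over x from 2 to 15 of P(X1 = x) · P(X2 ≥ 6 − x).

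R(0.10) = 0.0328 and R(0.30) = 0.8017. The stated 0.05 and 0.8 are met, so the sample-size arithmetic is correct.

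**Step 3. Effect of the gap.** Let s be the share of subjects in it. The documents do not give s; 4% (1 of 25), 10% and 20% (5 of 25) are assumptions. If these subjects cannot respond and the rest respond at the design rate, the overall rate is 0.30(1 − s) under the alternative and 0.10(1 − s) under the null.

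| s | Rate, alternative | Power | Rate, null | Type I error |
|---|---|---|---|---|
| 0 | 0.300 | 0.802 | 0.100 | 0.033 |
| 4% | 0.288 | 0.764 | 0.096 | 0.028 |
| 10% | 0.270 | 0.699 | 0.090 | 0.021 |
| 20% | 0.240 | 0.571 | 0.080 | 0.012 |

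Both error properties move in the conservative direction.

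**Step 4. Cost of opening the definition.** The added subjects have at least 4 baseline units and could halve their use by chance. As an assumed model, let units in the two eight-week windows be independent Poisson counts with a common mean, given a baseline of at least 4. The chance c that follow-up is at most half of baseline is 0.332, 0.181, 0.118 and 0.063 at means of 4, 6, 8 and 12. With no drug effect the overall rate is s·c + 0.10(1 − s).

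| s | Rate, c = 0.06 | Type I error | Rate, c = 0.33 | Type I error |
|---|---|---|---|---|
| 4% | 0.0984 | 0.031 | 0.1092 | 0.048 |
| 10% | 0.0960 | 0.028 | 0.1230 | 0.077 |
| 20% | 0.0920 | 0.023 | 0.1460 | 0.145 |

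If the added subjects respond at 10% under the null, like everyone else, type I error is the design value of 0.033.

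**The case against.** **The hemoglobin gate may be meant only for the hemoglobin-rise limb.** A transfusion-reduction limb is naturally for transfused subjects, and 5.2 files both entry routes under anemia. This may well be the intent. But one opening phrase governs both limbs in all four places, whereas the platelet definition in 8.1 names transfusion-dependent subjects explicitly. If the looser reading is intended, the fix only writes it down.

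**Few subjects are affected.** This stands. Section 5.2 expects most subjects to have both anemia and thrombocytopenia, and anyone who also qualifies on platelets or neutrophils keeps a route to response. So does a transfusion-dependent subject whose recorded hemoglobin is below 9.

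**The baseline blood count is already in the plan.** Partly right. Section 6.1 lists one within 72 hours of the first dose, but the response definition does not point to it.

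**The present text is conservative and the fix may not be.** Also true, as Step 4 shows; this cost has to be weighed.

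**A stronger reading is tempting.** Because 8.2 and the Precis endpoint paragraph omit the lineage rule and the limit to previously transfusion-dependent subjects, a reader might infer that the same subject could count as a responder just by keeping stable, untransfused platelets, so that type I error is inflated. The documents do not support that. Both paragraphs first define platelet responders by changes in platelet count or platelet transfusion need, and a never-transfused subject with a stable count has changed neither. Section 8.1, which sets out the criteria for the primary endpoint, supplies both limits. That reading would also reach every subject not receiving platelet transfusions, so it would not measure the erythroid gap at all.

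**Conclusion.** The mismatch is real on the text: entry and dosing accept two red-cell routes, and the response definition covers one. A subject who enters only by red-cell transfusion dependence, with recorded pretreatment hemoglobin of 9 g/dL or more, can only fail under 8.1. The consequence is lost power: 0.76, 0.70 or 0.57 against 0.80 designed, at assumed shares of 4%, 10% or 20%. These figures assume a 30% true response rate in the other subjects and none in this group. The true share is unknown and may be small. There is no inflation of type I error and no error in the Simon design. The point is worth correcting because the text is easily repaired and the decision rests on a small count, but confidence in its practical size is only moderate.

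**What to change.** For the primary-endpoint analysis:

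1. In both Precis paragraphs, 8.1 and 8.2, define erythroid response for subjects with pretreatment hemoglobin below 9 g/dL or red-cell transfusion dependence per 4.1.3.
2. Tie pretreatment hemoglobin to the baseline blood count in 6.1, and state that a subject who met the 4.1.3 anemia criterion at eligibility stays assessable for erythroid response.
3. As a consistency edit, repeat in the Precis endpoint paragraph and 8.2 the lineage rule and the platelet-limb limit that 8.1 already contains.

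The Simon boundaries stay as they are. The work is wording in four places. The statistical price is the chance-response risk in Step 4: negligible to modest at a small share, but up to 0.145 at a 20% share under the least favorable Poisson assumption shown.

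If any subject has already been assessed, report the primary result under both wordings. Excluding assessed subjects does not fit: 8.4 already leaves out the first 5, and 5 + 25 = 30 fills the accrual ceiling. The documents do not give current accrual.

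The same response criteria decide discontinuation (sections 3 and 8.6.2) and extended access (8.1). The sponsor must reconcile those passages with the corrected definition; no clinical rule is proposed here.
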